kinases- β (IKKs- β). We and others have demonstrated that aspirin can prevent or correct the insulin resistance associated with obesity.[37, 38] Pharmacologic modulation of arachidonic acid metabolites, such as aspirin, can positively modify lipid metabolism, increase HDL cholesterol. [39-41] Therefore in an attempt to test our hypothesis that the abnormal lipid values in Fontan patient reflect the presence of chronic inflammation, we plan to determine if the anti-inflammatory agent, aspirin, will normalize the lipid abnormalities in Fontan patients.

Protocol:

Patient Population: We plan to study 20 young adult subjects who have had Fontan repair of single ventricle. All subjects will be over 18 years of age and in good health. Individuals will be excluded if they have had active protein losing enteropathy within the past three years, have congestive heart failure, active arrhythmias, or on Coumadin. Any individual with a bleeding disorder or known esophageal varices will also be excluded. Subjects who known to have more than 10 drinks per week will be excluded. Females who are pregnant and /or planning become pregnant will be excluded.

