Protocol: After informed consent is obtained. Subjects will have fasting blood drawn for measurement of lipids, total cholesterol, HDL-Cholesterol, LDL-cholesterol and triglycerides, a complete metabolic panel, GGT, Complete blood count and differential, plasma insulin, inflammatory markers including sedimentation rate, high sensitivity C-reactive protein and haptoglobin. Individuals will also be asked to fill out the Short-Form 36 Quality of Life Survey. Individuals will be told to stop their current 81 mg/day of aspirin, and then be started on 650 mg (two 325 mg tablets) of aspirin 2 times a day. All aspirin will be provided by use. After two weeks of aspirin therapy all individuals will have a blood salicylate level taken 6 hours after their morning aspirin dose. Goal aspirin levels will be 15-20 mg/dl. If the level is less than 10 or greater than 20 mg/dl the aspirin dose will be adjusted. All individuals will be instructed into the early symptoms of aspirin toxicity include nausea, vomiting, tinnitus, and hyperventilation. If they should experience any of these symptoms they will be instructed to immediately call us. In addition, if the individuals have any excess bleeding, blood in their stool or abdominal pain they will be told to immediately call. After 8 weeks of aspirin therapy the individual will be asked to return for repeat fasting blood test including a salicylate level and repeat the Short-Form 36 Quality of Life Survey. In addition to measuring salicylate levels, drug compliance will be monitored by pill count. All individuals will be provided with more aspirin pills than necessary for the study. They will be asked to return all the unused aspirin pills and the number of remaining pills will be counted.

Statistical analysis:

This is a pilot study to determine the safety and feasibility of a larger randomized trial. This study will form the basis for a statistically valid sample size for this planned larger trial.

Our primary outcome variable will be a change in total cholesterol and HDL-Cholesterol. It is our hypothesis that aspirin therapy will result in an increase of either total cholesterol and/or HDL-cholesterol.

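### Does the week-8 salicylate level need a stated time since the last aspirin dose, as the week-2 level has?

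*Combined protocol and SAP*

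**What the plan says.** All the sampling text is in the Protocol section, in the paragraph that follows the patient population. Subjects are "started on 650 mg (two 325 mg tablets) of aspirin 2 times a day". The first salicylate level is tied to a dose: "After two weeks of aspirin therapy all individuals will have a blood salicylate level taken 6 hours after their morning aspirin dose". The target comes next, "Goal aspirin levels will be 15-20 mg/dl", and then the action limits: "If the level is less than 10 or greater than 20 mg/dl the aspirin dose will be adjusted".

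The second and last scheduled level is described differently: "After 8 weeks of aspirin therapy the individual will be asked to return for repeat fasting blood test including a salicylate level". The text does not say whether the morning dose is taken before that draw, how long after the last dose the sample falls, or whether either time is to be noted. The paragraph then gives the role of the levels: "In addition to measuring salicylate levels, drug compliance will be monitored by pill count".

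The Statistical analysis section sets the purpose, "This is a pilot study to determine the safety and feasibility of a larger randomized trial", and names total cholesterol and HDL-cholesterol as primary. The secondary outcomes are inflammatory markers, insulin and HOMA-IR, with quality of life and liver tests as further hopes. Salicylate concentration is not among them.

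**The concern.** A drug level means little without the time since the dose, and the protocol accepts this by fixing 6 hours at week 2. At week 8 the sample belongs to a fasting draw. Fasting allows a sample before the morning dose (about 12 hours after the evening dose, if doses are 12 hours apart), one soon after the morning dose, or one at 6 hours. A change between week 2 and week 8 could therefore reflect sampling time and not intake.

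Week 8 is also the only scheduled level after any week-2 dose adjustment, so it is the only one that could show whether an adjusted dose reached the goal. For a pilot that is to inform a larger trial, sustained exposure is a natural thing to report. If the times are not noted on the day, they cannot be recovered reliably.

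**Working it through.** The documents give no figure to reproduce, so the check has two parts: how far timing could move a reading, and whether any planned result uses that reading.

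**Inputs from the documents.** Dose 650 mg twice a day; week-2 sample at 6 h; goal 15-20 mg/dl; adjustment below 10 or above 20 mg/dl.

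**Assumptions, not in the documents.** Single-exponential decline with half-life *h* between 3 and 20 h, complete absorption by 2 h, and doses 12 h apart.

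**Size of the timing effect.**

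- A sample at 12 h relative to 6 h: ratio = 0.5^(6/*h*).
- A sample at 2 h relative to 6 h: ratio = 2^(4/*h*).

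| *h* (h) | 12 h / 6 h | 15 mg/dl reads | 20 mg/dl reads | 2 h / 6 h | 15 mg/dl reads |
|---|---|---|---|---|---|
| 3 | 0.25 | 3.8 | 5.0 | 2.52 | 37.8 |
| 6 | 0.50 | 7.5 | 10.0 | 1.59 | 23.8 |
| 12 | 0.71 | 10.6 | 14.1 | 1.26 | 18.9 |
| 20 | 0.81 | 12.2 | 16.2 | 1.15 | 17.2 |

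At 12 h, a subject at 15 mg/dl falls below the 10 mg/dl limit only if *h* < 6 × ln 2 / ln(15/10) = 10.3 h. A subject at 20 mg/dl falls below 15 mg/dl only if *h* < 6 × ln 2 / ln(20/15) = 14.5 h.

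**Which half-lives fit the protocol dose.** Take the same model at steady state, with 15 mg/dl at 6 h on the unadjusted dose. Each dose must raise the level by 15 × 2^(6/*h*) × (1 − 2^(−12/*h*)) mg/dl. The implied distribution volume is at most 650 / (10 × rise) litres, counting the whole 650 mg as salicylate.

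| *h* (h) | Rise per dose (mg/dl) | Volume at most (L) |
|---|---|---|
| 3 | 15 × 4 × 0.9375 = 56.3 | 1.2 |
| 6 | 15 × 2 × 0.75 = 22.5 | 2.9 |
| 12 | 15 × 1.414 × 0.5 = 10.6 | 6.1 |
| 20 | 15 × 1.231 × 0.340 = 6.3 | 10.3 |

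Volumes of 1.2 and 2.9 L are smaller than an adult's blood volume (general knowledge, not a figure in the documents). The rows for 3 and 6 h are therefore not credible for an adult at goal on this dose, although an upward-adjusted dose would relax the limit somewhat. The rows for 12-20 h are the usable illustration. There a 12-hour sample loses 19-29%, and 15 mg/dl reads below the goal but not below 10 mg/dl.

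**Which planned results use the week-8 level.**

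- *Dose adjustment.* The goal and limits follow directly on the week-2 level. No treatment beyond the 8-week visit is described, so at week 8 the limits have no later dose to act on.
- *Compliance.* Levels are used together with returned-tablet counts. A positive level shows intake whatever the interval.
- *Primary and secondary outcomes.* None uses salicylate concentration. Several need a fasting sample: HOMA-IR is built from fasting glucose and insulin, and lipids are drawn fasting at baseline. Fasting at week 8 therefore has its own reason.
- *Comparison of week 8 with week 2 or with the goal.* None is planned.

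**The case for a change.** The best argument for a change is that noting the time of the last dose and of the sample is cheap and alters no dose, goal or limit, while its absence cannot be repaired later. The pill count does not replace it, because tablets not returned say nothing about concentration. A low fasting level could also be misread as poor compliance.

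Much of this stands. The two sampling descriptions differ, timing alone can move a reading across the edge of the goal range, and a cautious site would note both times. Three things limit its weight.

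- What is lost is an extra use of the level (maintained exposure, success of an adjustment), not a result that the plan promises.
- The protocol's silence shows only that it does not call for the times to be recorded. Case report forms and laboratory procedures are not among the documents, so it does not follow that the times go unrecorded.
- Matching the intervals is not clearly cheap. A 6-hour level at a fasting visit needs either a fast lasting until 6 hours after the morning dose or a second blood draw. Moving the whole draw could shift its clock time relative to baseline for the lipids and insulin, which matter more here.

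**Conclusion.** No change follows. The week-8 level is untimed and nothing elsewhere in the document supplies the interval, but this is missing detail about a supporting compliance marker in a pilot planned for 20 subjects. With the plan followed as written, its primary and secondary results and its pill count are unaffected, and the level still does the one job assigned to it at week 8.

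The effect on the reading itself is moderate on credible assumptions: about 71-81% of the 6-hour value at 12 hours for a half-life of 12-20 h, so 15 mg/dl reads 10.6-12.2 mg/dl. If the fasting sample happens to fall at 6 hours, there is no difference. The figures rest on an assumed single-exponential decline, an assumed half-life and assumed 12-hour dose spacing.

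An analyst can fill the gap sensibly by reporting the week-8 level as evidence of intake beside the pill count. It should not be set against week 2 or the 15-20 mg/dl goal unless the dose-to-sample intervals are known and comparable.

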cholesterol has been identified as an important anti-inflammatory mediator [27], Zyblewski et al have speculated that the low levels of HDL-cholesterol observed in their study raises the possibility that single-ventricle patients may be in a chronic inflammatory state. We have also [28] demonstrated an abnormal lipid profile in Fontan patients. We reported that Fontan patients have decreased total cholesterol, LDL-cholesterol and HDL-cholesterol, while triglycerides remain normal. In a recent study we have demonstrated that the decrease in cholesterol is related to a decrease in biosynthesis that may be mediated by inflammation (our Fontan patients had significantly higher CRP's compared to our control subjects).(unpublished data) A similar lipid profile has previously been reported in individuals with rheumatoid arthritis. Amezaga-Urruela et al [29] reported a continuous decline in total cholesterol and LDL-cholesterol has been demonstrated during the 5 years prior to the development of rheumatoid arthritis and an increase in the total cholesterol/HDL-cholesterol ratio was also observed. Increasing CRP has been negatively associated with total cholesterol and HDL-cholesterol.[30] Furthermore, in rheumatoid arthritis, as inflammations decreases with therapy, lipid levels rise. [31, 32] Based on the similar lipid profile in Fontan patients with rheumatoid arthritis patients, we hypothesis that abnormal lipids in Fontan patients are an early marker of chronic inflammation.

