HDL-cholesterol levels may also relate to the pathogenesis of protein losing enteropathy. In the protein losing enteropathy patients in our study,[28]they had markedly low HDL-cholesterol and higher triglyceride levels. One determinate of HDL-cholesterol levels is lipoprotein lipase activity. [33] Blades et al [34]have reported that high hepatic triglyceride lipase and low lipoprotein lipase activity are both important contributors to low HDL-cholesterol levels in both normotriglyceride and hypertriglyceride subjects. In rheumatoid arthritis these is an inverse relation between lipoprotein lipase activity and inflammatory state. [35] Bode et al {Bode, 2005 #496} has demonstrated that loss of heparin sulfate proteoglycans from the basolateral surface of intestinal epithelial cells plays a central role in the pathogenesis of experimental meddles of protein losing enteropathy. Lipoprotein lipase is secreted by many tissues of the body, particularly metabolically active adipose tissue in the abdomen. It is transferred to the luminal surface of endothelial cells, where it is bound as homodimers to heparin sulfate proteoglycans and can be released by administration of heparin.{Lewis, 2005 #468} Therefore, if HDL-cholesterol levels are low in Fontan patients due to a decrease in lipoprotein lipases activity, based on Bode's report {Bode, 2005 #496} there may be a direct relationship between HDL-cholesterol level and protein losing enteropathy.

Abnormal lipoprotein lipase activity has also been speculated to relate to abnormal adipose tissue fatty acid trafficking and maybe part of the pathophysiological basis for ectopic fat deposition in the abdomen and heart. [36] We have recently demonstrated that Fontan patients have abnormally increased amounts of epicardial fat content when compared to age and body mass index adjusted group of patients with repaired tetralogy of Fallot. (Unpublished data)

Based on this review of the literature and our preliminary studies, we hypothesis that the abnormal lipid values in Fontan patient reflect the presence of chronic inflammation. Aspirin is a well-known agent that has been used to treat chronic inflammations associated with a number of diseases including Kawasaki's disease, rheumatoid arthritis and acute rheumatic fever. It has known to be well tolerated by both adults and children. Aspirin exerts some of its anti-inflammatory action by inhibiting the activity of I_KB

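### Does a primary hypothesis met by a rise in either of two lipids need a multiplicity rule in this pilot?

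*Combined protocol and SAP*

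**What the plan says.** The Statistical analysis section of the combined protocol and SAP defines the primary outcome as a single variable with two components: "Our primary outcome variable will be a change in total cholesterol and HDL-Cholesterol". The next sentence turns this into a directional hypothesis that one component can satisfy alone: "It is our hypothesis that aspirin therapy will result in an increase of either total cholesterol and/or HDL-cholesterol".

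The same section sets the purpose of the study: "This is a pilot study to determine the safety and feasibility of a larger randomized trial", followed by "This study will form the basis for a statistically valid sample size for this planned larger trial". The Patient Population paragraph gives the size: "We plan to study 20 young adult subjects who have had Fontan repair of single ventricle". There is one group, measured before treatment and after 8 weeks.

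The plan names no statistical test, significance level, sidedness, order of testing or adjustment for two primary lipids. It also sets no success criterion on which a decision would turn.

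**The concern.** The primary outcome joins the two lipids with an and, while the hypothesis joins them with an either. If each lipid is tested separately and either rise counts as support, the trial has two chances to succeed. The statement that the hypothesis was supported then has a higher false-positive rate than either test alone.

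The two lipids also mean different things. The Background gives HDL-cholesterol a rationale of its own ("there may be a direct relationship between HDL-cholesterol level and protein losing enteropathy", and aspirin-type agents "can positively modify lipid metabolism, increase HDL cholesterol"). For patients approaching rheumatoid arthritis it reports that "an increase in the total cholesterol/HDL-cholesterol ratio was also observed". A rise in total cholesterol alone is therefore not the same finding as a rise in HDL-cholesterol alone, yet the hypothesis treats both as support.

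At stake is a positive headline from the pilot that is easier to reach by chance than readers would assume, and that could be carried into the case for the larger trial.

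**Working it through.** The plan has no error rate or power calculation to reproduce, so the check asks how large the inflation is under each reasonable reading.

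**Inputs from the plan.** n = 20 (Patient Population); two primary lipids and only an increase counted (Statistical analysis).

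**Assumptions, not in the plan.** Paired t-test on each 8-week change (19 degrees of freedom); no true change in either lipid under the null, including none from time or regression to the mean; correlation between the two changes of 0 to 0.95. Because total cholesterol contains HDL-cholesterol, a positive correlation is plausible.

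**Step 1: uncorrelated changes.** The chance of at least one false increase is 1 − (1 − a)², where a is the upper-tail level per lipid.

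- One-sided 5% each: 1 − 0.95² = 9.75%.
- Two-sided 5% each, rises only (upper tail 2.5%): 1 − 0.975² = 4.94%.

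**Step 2: correlated changes.** Simulation with 1,000,000 null trials per correlation; critical values t > 1.729 and t > 2.093.

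| Correlation | One-sided 5% each | Two-sided 5% each, rises only |
|---|---|---|
| 0 | 9.7% | 4.9% |
| 0.3 | 9.3% | 4.8% |
| 0.5 | 8.8% | 4.6% |
| 0.7 | 8.1% | 4.3% |
| 0.8 | 7.6% | 4.0% |
| 0.9 | 6.9% | 3.6% |
| 0.95 | 6.3% | 3.3% |

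The first column exceeds 5% throughout and the second never does. The second is still above the 2.5% upper tail of a single two-sided test.

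**Step 3: what a Holm rule would change.** Holm at a one-sided family-wise 5% compares the smaller p-value with 0.05/2 = 0.025. That is the same event as a rise significant at two-sided 5%, so the chance of claiming at least one increase is the second column above, with no gain over unadjusted two-sided tests. If the first lipid passes, Holm tests the other at 0.05, which is looser than 0.025. Take a true rise of 0.66 SD in one lipid (detected at the first step with 80% power) and none in the other. With uncorrelated changes the unchanged lipid is claimed with probability 0.025 + 0.80 × (0.05 − 0.025) = 4.5%; simulation over the correlations gives 4.5% to 4.9%. Unadjusted two-sided tests give 2.5%.

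**Step 4: what Holm would cost against unadjusted one-sided 5% tests.** The change detectable with 80% power (non-central t) rises from 0.577 SD at one-sided 5% to 0.660 SD at the first Holm step. The chance of claiming at least one increase changes as follows.

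| True changes (SD) | Unadjusted one-sided | Holm | Loss |
|---|---|---|---|
| 0.66 and 0 | about 89% | about 80% | about 9 points |
| 0.5 and 0 | about 70% | about 57% | about 13 points |
| 0.5 and 0.5, correlation 0 | 91% | 81% | 10 points |
| 0.5 and 0.5, correlation 0.9 | 76% | 64% | 12 points |

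**Step 5: what is untouched.** The mean changes and SDs do not depend on how the hypothesis is judged, so the figures passed to the sample-size calculation for the larger trial are the same with or without a rule.

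**The case for a change.** The strongest case for a change is that the hypothesis is directional, so a one-sided test is a natural reading. On that reading the rate exceeds 5% at every correlation examined, and is still 6.3% at 0.95. The end of the Background presents the study as a test of the inflammation hypothesis, so the pilot label does not remove all interest in a yes-or-no answer. A false-increase rate that runs from about 3% to 10% according to unstated choices is itself a reason to state them, and doing so takes a few sentences and no extra patients. If movement in either direction were counted under two-sided 5% tests, the rate would be about 10% down to 6.5%.

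Part of this stands. The rule is missing, and a single statement of support would hide which lipid moved. But a directional hypothesis does not commit the analyst to a one-sided 5% test, and counting falls as well as rises would contradict the hypothesis as worded. The Background passages on HDL-cholesterol argue for reporting the two lipids separately, not for adjusting alpha. With one group and no control, a supported result could also reflect time or regression to the mean, and no alpha rule makes it attributable to aspirin.

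**Conclusion.** No change to the plan follows. The either-or wording and the absence of a multiplicity rule are real, but this is a gap in a small, uncontrolled pilot that analysts would fill sensibly: give both 8-week mean changes with unadjusted 95% confidence intervals as pilot estimates, and say which lipid or lipids rose. If no formal test is intended, no multiplicity rule is needed.

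The size depends on the unstated test. With n = 20, paired t-tests and correlation 0 to 0.95, the chance of at least one false increase is about 10% down to 6% at one-sided 5% per lipid, and about 5% down to 3% with two-sided 5% tests where only rises count. Should the sponsor want a formal claim, the two-sided reading already holds the rate at or below about 5%, so Holm is optional. Imposing it would trade about 9 to 13 points of power against unadjusted one-sided testing for a modest reduction in error, a choice on which reasonable statisticians would differ.
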